10.3 Subject Satisfaction using Face-Q Questionnaires

FACE-Q, User's Manual, version 1.0, January 2015 (see Section 22.1).

10.3.1 Satisfaction with Outcome

In the section of the User's manual, "Process of Care Scales", the questionnaire about the "Satisfaction with Outcome" will be used: This scale measures a subject's satisfaction with the result of their most recent procedure.

"Satisfaction with Outcome" assessments will be performed by the subject at Week 12 (Visit 4), at Week 24 (Visit 5), at Week 36 (Visit 6) and/or at Week 48 (Visit 7) and/or Visit 7c.

Separate assessments will be performed for the left and the right side of the face.

10.3.2 Appraisal of Nasolabial Folds

In the section of the User's manual, "Appearance Appraisal Scales", the questionnaire about the "Appraisal of Nasolabial Folds" will be used.

"Appraisal of Nasolabial Folds" assessments will be performed by the subject at Week 12 (Visit 4), at Week 24 (Visit 5), at Week 36 (Visit 6) and/or at Week 48 (Visit 7) and/or Visit 7c.

[figure not shown]
Separate assessments will be performed for the left and the right side of the face.

10.4 Subject's Evaluation of Pain

The subject's perception of pain will be evaluated for treatments with Princess® FILLER Lidocaine and Juvéderm® Ultra XC.

This evaluation will be assessed using a scale adapted from the 11-point NPRS, where "0" indicates "no pain" and "10" indicates "the worst pain imaginable".

The evaluation of subject's pain will be done starting 15 min (+/- 3 min) after last injection and at 15 min-intervals (+/- 3 min) for 60 min (+/- 3 min) post-treatment (initial and repeat-treatments) using the adapted NPRS.

10.5 Injection Volume

For each subject, the total volume injected will be recorded separately for each treatment (initial, touch-up and repeat-treatments).

10.6 Time to Repeat-Treatment

For each subject, the time from initial treatment to repeat-treatment will be recorded for each investigational group and assessed by tabulating the following rates:

- Repeat-treatment at Week 36
- Repeat-treatment at Week 48
- Repeat-treatment at Visit 7c
- No repeat-treatment

10.7 Clinical Photography

Clinical photography of the subject's face will be taken at Screening (Visit 1), on Day 0 (Baseline) and at Week 12, 24, 36 and/or 48 and/or Visit 7c after initial treatment (at Visit 2, 4, 5, 6 and/or 7 and/or Visit 7c, respectively) under standardized conditions in accordance with the manual. On treatment days (initial- and/or repeat-treaments), the clinical photography will be performed prior to the treatment.

10.8 Visual Examinations

Visual examinations (including Snellen visual acuity, confrontational visual fields and ocular motility) will be performed at the study site by the examiner (i.e. treating investigator or authorized designee) prior to- and 30 min after any treatment (after all other assessments have been performed) at:

- o Baseline (Visit 2)
- Week 2 (Visit 3a) (only in case of touch-up treatment)
- o Week 4 (Visit 3b)
- Week 6 (Visit 3c) (only in case touch-up treatment was performed at Week 2 [Visit 3a])
- Week 36 (Visit 6) or Week 48 (Visit 7) or Visit 7c (only in case of repeat-treatment)
- Week 40 (Visit 8a) or Week 52 (Visit 8b) or Visit 8c (only in case repeat-treatment was
 performed respectively at Week 36 [Visit 6] or Week 48 [Visit 7] or Visit 7c)
- Week 48 (Visit 9a) or Week 60 (Visit 9b) or Visit 9c (only in case repeat-treatment was performed respectively at Week 36 [Visit 6] or Week 48 [Visit 7] or Visit 7c)

All visual examination results and the use of corrective eyewear (i.e., glasses/contact lenses) will be recorded on the eCRF.

[figure not shown]
10.8.1 Snellen Visual Acuity

Visual acuity for each eye will be assessed using the standard Snellen hanging wall chart (Figure 1).

CPH-301-201200F

15 Mar 2021

Figure 1: Standard Snellen Hanging Wall Chart

The assessment will be carried out as follows:

- The standard Snellen hanging wall chart will be read with the subject standing at a distance of 20 feet (6 meters).
- Each eye will be tested independently (i.e. one eye will be covered while the other eye will be used to read).
- If applicable, the subject should wear the same corrective eye wear (i.e. glasses/contact lenses) at each assessment.
- The ability to read every line on the chart does not need to be assessed. It is acceptable to move directly to the smaller characters, where appropriate.
- The numbers at the end of the line indicate the subject's visual acuity compared with a subject with normal visual acuity:
 - o Normal limits are 20/25 or better, with no acuity difference between the eyes
 - o The larger the denominator, the worse the acuity
 - o 20/200 = subject sees at 20 ft (6 meters) what an individual with normal visual acuity sees at 200 ft (60 meters)
 - Results will be recorded in the eCRF as normal or abnormal alongside the actual Snellen results in numerical form for both eyes

10.8.2 Confrontational Visual Fields

The confrontational visual fields will be used to assess peripheral vision for each eye. The assessments will be made as follows:

STRICTLY CONFIDENTIAL

Correct positioning

- The examiner should be eye level with the subject, separated by approximately 8 to 12 inches (20 to 30 cm).
- The subject should remove corrective eyewear (i.e. glasses/contact lenses).
- The examiner will cover one eye and the subject will cover the one opposite. The open eyes should then be staring directly at one another.

Technique

- The examiner will present finger(s) in each of 4 quadrants, taking care not to position fingers in overlapping quadrates.
- With head stationary the subject will be asked to correctly identify the number of fingers.
- All 4 quadrants (upper and lower, temporal and nasal) must be tested.
- The test will be repeated with the opposite eye open.

10.8.3 Ocular Motility

The movements and alignment of eyes will be tested for each eye by evaluation of ocular motility as follows:

- The examiner will stand in front of the subject.
- The subject should remove corrective eyewear (i.e. glasses/contact lenses).
- The subject will be asked follow examiner's finger with their eyes while keeping their head in one position.
- The examiner will trace an imaginary "H" or rectangular shape in front of them, making sure that the finger moves far enough out and up/down so that all appropriate eye movements can be seen (lateral up, lateral down, medial down, medial up).
- Then the finger will be brought directly in towards the subject's nose. This will cause the subject to look cross-eyed and the pupils should constrict (accommodation).
- The eyes should be able to easily and smoothly follow the examiner's finger.
- The results of the test will be documented for both the left and the right eye.

10.8.4 Abnormal Visual Examinations

The following results from visual examinations at Baseline will be considered abnormal and will exclude the subject from participation in the study:

- Snellen acuity test: any result worse than 20/40 (with corrections, if applicable)
- Confrontational visual field test: abnormal is defined as the inability of the subject to correctly identify/count the examiner's fingers in one or more quadrants in one or both eyes.

Ocular motility: abnormal is defined as the inability of the subject to follow the
finger of the tester smoothly; inability to focus on the finger as it points to the nose;
any unexpected and/or uncontrolled eye movements such as nystagmus or divergent or
unilateral strabismus

Should any of the vision assessments (Snellen visual acuity, confrontational visual test field, or ocular motility) suddenly worsen after the injection of the filler, the treating investigator must examine the subject to exclude vascular injection and contact an eye specialist if necessary.

In addition, any one of the following changes in visual examinations after Baseline will be considered abnormal and clinically significant:

- Snellen acuity test: any change of 1 line or more
- Confrontational visual field test: change to the peripheral vision
- Ocular motility: change to ocular motility

If any of the above changes occur at any assessment, the change should be reported as an AE and the subject must be referred to an ophthalmologist to evaluate if the resulting change is related to a vascular injection of the dermal filler. If the ophthalmologist confirms that the the result is related to a vascular injection of the dermal filler, the subject should be treated per standard of care for intravascular injection of dermal filler. The subject will be withdrawn from the study and the need for stopping the study will be reviewed.

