12.1 Definitions of Adverse Events and Adverse Device Effects

Adverse Event (AE)

An AE is defined as any untoward medical occurrence, unintended disease or injury or any untoward clinical signs in subjects, users or other persons. This definition includes events whether or not related to the IMDs and those events related to the procedures involved.

Adverse Device Effect (ADE)

An ADE is defined as an AE that is related to the use of the IMDs. This includes any AE resulting from insufficiencies or inadequacies in the IFU, the deployment, the implantation, the installation, the operation, or any malfunction of the IMDs. In addition, this includes any event that is a result of a use error or intentional misuse of the IMDs.

Those AEs occurring after provision of informed consent and prior to application of the IMDs will be recorded as part of the medical/aesthetic procedures history. Any medical condition that is present at the time that the subject is screened should be also considered as medical/aesthetic procedures history and not recorded as an AE (see Section 10.9). However, if the condition deteriorates at any time from date of administration of the IMDs during the clinical investigation, it should be recorded and reported as an AE.

For a list of anticipated AEs and anticipated ADEs please refer to Section 6.1. In addition, the following events could specify as Adverse Events of Special Interest (AESI);

- Changes in vision (i.e. loss of vision, blurriness, double vision, pain in or around your eye, blindness, blind spots, problems moving the eyes, change in peripheral vision)
- Skin changing color around the eyelids or around the site of injection

Serious Adverse Event (SAE)

An SAE is defined as an AE meeting one or more of the following conditions:

- led to death
- led to serious deterioration in health of the subject that either resulted in:
 - o a life-threatening illness or injury, or

- o a permanent impairment of a body structure or a body function, or
- o in subject hospitalization or prolonged hospitalization, or
- o medical or surgical intervention to prevent life-threatening illness or injury or permanent impairment to a body structure or a body function
- led to fetal distress, fetal death, or a congenital abnormality or birth defect
- is an important medical event

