- 9 Repeat-treatment at Week 36 (Visit 6) OR Week 48 (Visit 7) OR Post repeat-treatment hold Follow-up (Visit 7c)
- 10 Only if repeat-treatment occurred at Week 36 (Visit 6) OR Week 48 (Visit 7) OR Post repeat-treatment hold Follow-up (Visit 7c)
- 11 All subjects must be asked if they are experiencing or have experienced any signs/symptoms of vision changes or stroke since the injection
- 12 Exclusion criterion based on visual examinations at Baseline
- 13 If a subject was not evaluated for repeat-treatment at Week 36 (Visit 6) and/or Week 48 (Visit 7) due to the hold on repeat-treatment, the subject could attend Visit 7c for evaluation and repeat-treatment (if eligible)
- a Includes information on prior medication, defined as all medication taken/received within the previous ten days
- b Includes date of birth, sex, race and ethnicity
- c Visual examinations (including Snellen visual acuity, confrontational visual fields and ocular motility) to be performed at Baseline and at Week 4; in case of touch-up treatment, to be performed at 4 and 12 weeks after repeat-treatment visit. To be performed prior to- and 30 min after any treatment after all other assessments. The subject should wear the same corrective eyewear (i.e. glasses/contact lenses) at each assessment, if appropriate. The definition of clinically significant changes and action to be taken is presented in Section 10.8.4 of the protocol.
- d In women of childbearing potential only, including those who are postmenopausal for less than twelve months
- e Evaluation and grading of nasolabial folds severity by the treating investigator and by the independent blinded evaluating investigator (separate assessments) will be done using the 5-point NLF-SRS. The Baseline severity is the severity grade assigned at Screening as determined by the treating investigator in conjunction with the independent blinded evaluator. The left and right cheek will be separately evaluated.
- f Clinical photography will be performed; the evaluation and grading of nasolabial folds severity by the independent blinded photographic reviewers using the 5-point NLF-SRS and based on photographs will take place at the end of the clinical investigation. The left and right cheek will be separately evaluated
- g Evaluation of subject satisfaction using the FACE-Q questionnaire "Satisfaction with Outcome"
- h Evaluation of subject appearance appraisal using the FACE-Q questionnaire on "Appraisal of Nasolabial Folds"

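### Minor: the post-Baseline Snellen trigger in Protocol 10.8.4 has no direction, so read literally a one-line gain in acuity leads to an AE report and a mandatory ophthalmology referral

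*Protocol*

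**What the plan says.** Protocol 10.8.4 contains three rules. The first excludes subjects at Baseline, including those with acuity worse than 20/40. The second applies after treatment and has this condition: "Should any of the vision assessments (Snellen visual acuity, confrontational visual test field, or ocular motility) suddenly worsen after the injection of the filler". When it is met, a check for vascular injection is required, with an eye specialist involved if needed. The third follows directly: "In addition, any one of the following changes in visual examinations after Baseline will be considered abnormal and clinically significant". Its acuity item is "Snellen acuity test: any change of 1 line or more", and its two other items, on peripheral vision and ocular motility, are also worded simply as changes. If any listed change occurs at any assessment, "the change should be reported as an AE and the subject must be referred to an ophthalmologist", so that the ophthalmologist can judge whether a vascular injection caused it.

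Protocol 10.8 schedules these examinations "prior to- and 30 min after any treatment (after all other assessments have been performed) at" a list of visits. Protocol 10.8.1 states that a larger denominator means worse acuity, and on recording it says: "Results will be recorded in the eCRF as normal or abnormal alongside the actual Snellen results in numerical form for both eyes".

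Protocol 12.1 defines an AE as "any untoward medical occurrence, unintended disease or injury or any untoward clinical signs in subjects" and others.

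In the SAP, a footnote to the schedule in 2.10 says: "The definition of clinically significant changes and action to be taken is presented in Section 10.8.4 of the protocol". SAP 9.4 plans shift summaries of visual outcomes, from pre-treatment on treatment days and from Baseline on other days, plus listings.

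**The concern.** A safety trigger should fire on possible harm. This one fires on any movement of a line, and once it fires the protocol leaves the investigator no room to judge relevance. A one-line gain would then enter the AE data as an event and send the subject to an ophthalmologist to look for a vascular accident that an improvement gives no reason to suspect.

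Gains are possible. Acuity down to 20/40 is accepted at Baseline, whereas 10.8.1 sets normal at 20/25 or better. The same section lets the examiner go straight to smaller characters, so the path down the chart need not be the same at each visit.

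At stake are non-harm events in the overall AE tables and unneeded referrals. There is also an awkward position for sites: under 17.2 a failure to follow the plan is a deviation, so a site that sensibly does not refer a subject with a gain is technically in breach.

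**Working it through.** The plan gives no figure on this point, so the check is a comparison of texts.

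**Step 1: the three rules in 10.8.4.**

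| Rule | Direction stated? | Consequence |
|---|---|---|
| Baseline exclusion | Yes, worse than 20/40 | Not enrolled |
| Sudden change after injection | Yes, worsening | Investigator examines; eye specialist if needed |
| Listed post-Baseline changes | No | AE report (should) and ophthalmologist referral (must) |

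The section uses directional wording in the first two rules and not in the third. The third is joined to the second by an additive phrase, so the worsening condition does not carry over to it.

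**Step 2: apply the third rule to a gain.** Take an eye at 20/30 at Baseline and 20/25 at Week 4 (illustrative, assuming these are adjacent lines on the chart). By 10.8.1 the smaller denominator is better. The reading has changed by one line, so the rule is met.

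**Step 3: compare with 12.1.** An AE there must be untoward. Better acuity is not. The two sections give different answers for the same reading.

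**Step 4: look for a restriction elsewhere.** Protocol 9.1.2, 9.2.2, 9.3, 10.8.1, 12.1 and the schedule footnotes, and SAP 2.10 and 9.4, were read for any limit to loss. None was found. Protocol 9.3 and both schedules point back to 10.8.4.

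**Step 5: check what a directional rule must still catch.** The bullet names no reference reading. Suppose an eye is 20/40 at Baseline, 20/25 just before repeat-treatment and 20/40 at 30 minutes afterwards (illustrative).

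- Against Baseline alone: 20/40 to 20/40, no loss, so no trigger.
- Against the same-day pre-treatment reading: 20/25 to 20/40, a loss, so the trigger fires.

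A rule tied to Baseline alone would drop the AE instruction and the mandatory referral for a real post-injection loss. Taking the better of the two readings as reference keeps both.

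**Step 6: size.** The number of gains needs a rate of test-retest variation or true improvement, and the documents give none. No count is derived.

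**The case against.** The strongest reply is that context already supplies the direction. The section is headed as concerning abnormal examinations, the referral exists only to detect vascular injection, and 12.1 can be read as filtering out anything not untoward. An over-inclusive trigger is also a defensible choice where the feared harm is blindness. As evidence of intent this is persuasive: a loss was very probably meant. It does not alter the trigger as written, which declares the change significant without further judgement. If breadth was deliberate, the text should say so, because 12.1 points the other way.

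Two further objections stand in full. A fix tied only to Baseline would weaken protection, as step 5 shows. Correcting the Snellen bullet alone would leave the two companion bullets just as undirected.

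Some stronger readings are tempting but not supported:

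- *A large number of false AEs.* A reader might count examinations. For 270 subjects with initial treatment only, two examinations after injection and two eyes give 270 × 2 × 2 = 1,080 readings. If the 30-minute examination is treated as part of Baseline, it is 270 × 1 × 2 = 540. Either figure counts readings, not gains. Many may also predate the current text: version 7.0 is dated 15 March 2021, first visits were anticipated in the first half of 2019, and whether the one-line wording existed then cannot be seen.
- *Forced withdrawal.* Under 10.8.4 this needs an ophthalmologist to confirm a vascular injection. Protocol 9.3 only says that subjects may be discontinued for such changes.
- *Inflated AESIs.* The vision items in 12.1 describe harms. The one neutral item concerns peripheral vision, not acuity.
- *Lost repeat-treatment.* The second exclusion in 9.2.2 mentions visual changes without direction, so a recorded gain could raise a question. But it pairs them with other serious medical conditions and does not cite 10.8.4.
- *An analysis that cannot separate gains from losses.* A shift table can show direction, individual results are listed, and the table shells are in a separate document not available here. The SAP footnote annotates a schedule and is not an analysis rule.

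**Conclusion.** The bullet is wrong as written, and the point is minor. Read literally, it makes a one-line improvement a reportable AE with a compulsory referral, contrary to 12.1 and to the purpose of the referral.

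The error runs toward over-reporting, so no true loss is missed. Effectiveness endpoints are untouched. SAP 9.3 summarizes AEs other than injection site reactions for both devices together, so the device comparison is unaffected. Event terms and the recorded Snellen values may let a reader of the listings recognize a gain.

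The conclusion rests on the plain wording of 10.8.4 and on finding no limiting text elsewhere in the two documents. It does not rest on any assumed frequency of gains or on how sites in fact applied the rule, which the documents do not show.

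**What to change.** In Protocol 10.8.4:

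1. Replace the Snellen bullet with: *worsening (loss) of 1 line or more in either eye, compared with Baseline or with the same-day pre-treatment examination, whichever reading is better*. At visits without treatment the reference is then Baseline, as in SAP 9.4.
2. Reword the other two bullets as *worsening of peripheral vision* and *worsening of ocular motility*.
3. Leave the sudden-worsening rule unchanged.

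Optionally, in SAP 9.4, derive signed line change per eye from the numerical Snellen values, using the references that section already names. Tabulate losses and gains of one line or more separately, if the shells do not already do this. If the conduct wording can no longer be changed, this SAP step can be taken alone.

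The cost is three short wording changes in a safety section revised at FDA request, so the agency would need to see that no loss escapes the new rule. The SAP option needs one derived variable and two table rows, and no new data, since the readings for both eyes are already in the eCRF.

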10.9 Other Assessments

Each of the following information have to be listed in the subject's medical record and recorded on the eCRF:

- **Demography**: includes date of birth, sex, race and ethnicity collected at Screening (Visit 1); every effort will be made to enroll male subjects in sufficient numbers.
- Medical/aesthetic procedures history: collected from both subject interview and medical records at Screening (Visit 1).

Particular attention should be paid to:

- Diseases and medical conditions addressed in exclusion criteria
- Previous aesthetic and surgical procedures in the treatment area

STRICTLY CONFIDENTIAL

All medications taken by the subject in the previous ten days (regularly or
occasionally), including over-the-counter and herbal medicines, and with special
attention to immune therapies, anticoagulant drugs, antiplatelet drugs, and analgesics

All co-morbidities, major surgeries, aesthetic dermatology procedures in the previous year (e.g. skin resurfacing procedures, needling, mesotherapy, or similar), all medications taken within the previous ten days, and, in females, the date of the last period will be recorded in the eCRF.

• Prior and concomitant medications/treatments: Prior medications/treatments are defined as all medications/treatments taken/received within ten days (whether continuing or not) prior to Day 0. Particular attention should be made to identify the use of anti-coagulation or anti-platelet agents (e.g. acetylsalicylic acid). Concomitant medications/treatments is defined as all medication taken/received from Day 0 (including medication taken immediately pre-injection and post-injection) until the last visit.

At each visit or phone call, the subject must be asked about any new medication taken or changes in current medication, as well as any aesthetic procedure applied in the area treated with the investigational devices.

On treatment days (Visit 2, 3a, 6 or 7 or 7c), information on concomitant medications/treatments will be collected before the dermal filler injection procedure.

All prior and concomitant medications/treatments will be recorded in the eCRF

- **Fitzpatrick skin types**: to be documented at Screening (Visit 1); every effort will be made to include individuals with all Fitzpatrick skin types, included types V and VI.
- Randomization: will only occurr via IVRS/IWRS once eligibility has been confirmed by the site.

Treatment: Initial, touch-up with the assigned device following randomization scheme will be applied according to this CIP. The repeat-treatment will be performed with Princess[®] FILLER Lidocaine on both NLFs.

- Adverse events: Occurrence of adverse events will be collected at each visit after the initial treatment at Baseline (Visit 2), from Visit 2 to Visit 9a, 9b or 9c included (for more information, see Section 12).
- Urine pregnancy test: Required in women of childbearing potential only, including those who are postmenopausal for less than twelve months. An urine pregnancy test (dip stick) will be performed at Screening (Visit 1), prior to initial treatment (Day 0/Visit 2), prior to touch-up treatment (Week 2/Visit 3a) and prior to repeat-treatment (Week 36/Visit 6, Week 48/Visit 7 or Visit 7c).
- Weight measurement: at Baseline (Day 0/Visit 2), at Visit 3a, 3b, 3c, 4 and 5, as well as at Visit 6, Visit 7 or Visit 7c upon evaluation for repeat-treatment; as well as Visit 8a/8b/8c or Visit 9a/9b/9c; weight measurement should be done to the nearest 0.1 kg and with the subjects standing barefoot and wearing light indoor clothing.
- Subjects' daily safety diary: to be dispensed to each subject at the end of each treatment session (and additionally at Week 4/Visit 3b for subjects having received touch-up treatment at Week 2/Visit 3a) in order to record injection site reactions, as well as the incidence of adverse events and AEs associated with the unintended intravascular injection; to be collected and reviewed two and four weeks after initial-/touch-up treatment (and additionally at Week 6/Visit 3c), and four weeks after repeat-treatment.

The diary will include the following adverse events:

- Changes in vision (i.e. loss of vision, blurriness, double vision, pain in or around your eye, blindness, blind spots, problems moving the eyes)
- Skin changing color around the eyelids
- o Crusty or scabby skin around the eyelids
- Headache
- o Fever
- Dizziness
- Confusion
- Weakness or numbness in the arms or legs
- o Changes to consciousness or alertness
- O Difficulty speaking/speech impairment

- Face droop
- Changes to chewing and drinking
- o Discomfort and discomfort with palpation
- Sensitivity to hot/cold liquids and foods

Furthermore, the subject diary will include specific instructions to seek immediate medical attention if any of the above symptoms or signs is observed.

